2. BACKGROUND AND RATIONALE

2.1 Background on Condition, Disease, or Other Primary Study Focus

Prevalence of OUD among pregnant and parenting women in NH is high and costs of untreated OUD are high. Perinatal OUD is described as a national public health epidemic, and NH is no exception.⁸ Roughly 40% of recent opioid overdose deaths in the state were women, and 21% of pregnancy-associated deaths between 2013-2015 were attributed to overdose. An estimated 8-10% of deliveries in NH are affected by perinatal OUD. Rising prevalence rates indicate that NH can anticipate as many as 1,000 infants born with prenatal opioid exposure each year. Perinatal OUD is associated with increased morbidity and mortality for both mother and infant due to infectious disease, higher rates of prematurity and pregnancy complications, low birth weight, neonatal abstinence syndrome (NAS), and social stressors such as homelessness, poor nutrition, and criminal justice involvement. In 2012, nearly 22,000 neonates in the U.S. were born with NAS, translating to one neonate born every 30 minutes and resulting in \$1.5 billion in hospital charges nationwide. Prenatal substance exposure and untreated postpartum maternal substance use are associated with developmental disorders and risk of adverse childhood experiences for children, which are strong predictors of later adolescent and adult substance use disorders and related health consequences.

The current standard of care for treatment of OUD during pregnancy is medication for opioid use disorder (MOUD) with methadone or buprenorphine. Evidence indicates buprenorphine improves neonatal outcomes compared with methadone in terms of lower NAS risk, shorter NAS treatment duration and mean length of hospital stay, higher mean gestational age, and greater weight, length, and head circumference at birth. Medication is most effective in combination with counseling, care management, and psychosocial support to address the complex array of individual and social factors that can adversely impact treatment compliance and the health and wellbeing of women and their children. Expansion of MOUD in obstetric settings for pregnant and parenting women with OUD is a targeted priority of the NH State Targeted Response (STR) to the opioid crisis.

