3. STUDY DESIGN

Activities to meet Aim 1. We will evaluate MMORE in a two-group randomized controlled design comparing treatment as usual (TAU) in partner maternity care practices with TAU + MMORE.

Participants will be 150 English-speaking consenting pregnant women aged 18 years and over who have a confirmed singleton pregnancy and are receiving perinatal services and medication for opioid use disorder at partner maternity care practices. We will aim to recruit women in their 2nd/early 3rd trimester of pregnancy.

After completion of the baseline assessment, consented participants will be randomly assigned to participate in the 8-session virtual yoga-mindfulness group intervention or to receive TAU only.

All intervention participants will be provided with a unique password-protected access link to the digital support materials, as well as detailed instructions for how to access the materials. A unique study code will allow us to monitor individual participant use of the support modules for analytic purposes.

All consented participants will complete assessments at baseline, post-intervention (8 weeks for TAU participants) and 3 months postpartum. Participants will complete assessments via a secured, de-identified and password-protected link accessed either on a study-provided laptop computer at a scheduled practice visit or via a protected email link to the user for completion at home or on another secure device with Internet access. Assessments will take approximately 20 minutes to complete. Based on formative data from phase 1 of this project, and other work the research team has conducted with the target population, we anticipate most women will have some access to the Internet either via a mobile phone, tablet, or home computer. If a participant cannot complete an assessment online, a paper version will be provided. The study staff will track ways that participants complete assessments. Participants will receive local gift cards for completion of each assessment.

Activities to meet Aim 2. All study participants (TAU and TAU+MMORE) will complete brief mobile assessments at the end of each week of their assigned cohort period. Assessments will be completed using either a mobile device or computer. Participants will receive a prompt (near end of the week) to complete the assessment. The encrypted, password-protected weekly brief assessment will include items to assess the following:

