We have developed a safety protocol (overseen by Drs. [name] and [name]) to ensure strict attention to safety for women participating in the yoga intervention. As with other gentle yoga protocols, the safety protocol will include specific directions by the Intervention Instructor that participants do not have to partake in any of the poses or activities that feel uncomfortable, and adjustments will be made as needed to minimize discomfort for those participants that would like such adjustments. Lead Instructor [name] has over six years of experience leading trauma-sensitive yoga protocols with pregnant incarcerated women, a vulnerable population similar to that for the proposed project.

The Lead Instructor will complete the Session Event Checklist after each intervention session to denote any adverse events (non-serious and serious) that take place during the intervention sessions. Participants will complete the Intervention Experience Form at the end of each session to document experience of any adverse events including physical experiences (e.g., shortness of breath, pain, increased or decreased infant movement, or other discomfort experiences during the session) and psychological experiences (e.g., emotional flooding, uncontrollable crying). At the end of each intervention week, all participants will also complete a Weekly Monitoring Form that will include items related to any additional experience of adverse physical or psychological events. The project coordinator will administer the Weekly Monitoring Form by telephone or e-mail.

In the event that a study participant lapses or relapses during the study period, cases will be handled on an individual basis, which may be largely determined by the procedures of the partner maternity care practice in terms of preference for ongoing care. A lapse/relapse will not necessarily lead to participant discontinuation in the study.

Treatment as Usual. Treatment as usual is operationalized as the integrated medication assisted treatment being provided at the partner practice as part of the New Hampshire State Targeted Response 21st Century Cures initiative. Such treatment includes medication for opioid use disorder, individual and/or group counseling, and case management.

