MOUD Treatment Retention. Treatment retention will be operationalized as a composite of medication adherence (number of weeks buprenorphine or methadone present in the urine toxicology report) and treatment adherence (number of weeks attended required counseling as part of comprehensive treatment as usual, as indicated in clinical notes) - throughout the prenatal period to 3 months postpartum.

Opioid use abstinence. Weekly point of care urine toxicology screening is conducted as part of standard care with all MOUD patients at partner practices to assess for THC, cocaine, benzodiazepines, methamphetamine, opioids, methadone and buprenorphine. Opioid abstinence will be measured as number of weeks consistently abstinent from opioids over the perinatal period to 3 months postpartum.

Secondary End Points:

Other substance use. Other substance use will be measured as number of weeks the participant used marijuana and/or other drugs as indicated in urine toxicology reports. Tobacco and alcohol use will be measured by way of documentation in clinical notes from visits.

Participant Self-Report Procedures: Participants will complete secured online survey assessments at baseline, post-intervention, and 3-months postpartum. The project coordinator will ensure that participants receive the assessment surveys at the specified times in the manner preferred by the participant. If participants wish to receive the survey via email, the survey will be sent as a unique study-identified password-protected link. The project coordinator will monitor and track survey assessment completion and ensure that participants receive gift card incentives for survey completion in a timely manner. For participants who do not wish to complete the survey online, the project coordinator will arrange for either a phone interview with the participant to complete the survey or will mail the participant the survey along with a self-addressed and stamped envelope for the participant to return the survey. The assessment survey will include the following:

Primary End Points:

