Treatment Retention. Self-reported adherence to medication for opioid use disorder will be assessed by an adaptation of items from the well-established Adherence to Medication questionnaire originally developed for assessing adherence to antiviral medications among persons with HIV/AIDS. (i.e., when was the last time you skipped buprenorphine medication? [past 2 days, within the past 2 weeks, 2-4 weeks ago, 1-3 months ago, never skipped past 3 months]. Participants will also report how often they attended group/individual counseling in the past 3 months [every week, every other week, once a month, less than once a month].

Opioid abstinence. The reliability of self-report of substance use for pregnant and parenting women is especially complicated due to well-founded fears of child protective service involvement and potential loss of children. That said, when research studies are well-conducted and assurances for protection of participant privacy are clear and conveyed with messaging informed by community partners with lived experience, women do reliably self-report their use behaviors.

Opioid use will be assessed with relevant items from the Alcohol, Smoking and Substance Involvement Screening Test, aligned with relevant timeframes (baseline: past 6 months, post-intervention and 3 month postpartum: past 3 months). Opioid use disorder severity will be assessed with items corresponding to DSM-V diagnostic criteria.

Secondary End Points:

Other substance use:

Self-reported frequency and quantity of opioid and other substance use (including alcohol, marijuana, and tobacco) will be assessed with the Alcohol, Smoking and Substance Involvement Screening Test, aligned with relevant timeframes (baseline: past 6 months, post-intervention, 3 month postpartum: since last survey).

Mental Health:

Depression will be assessed using the Edinburgh Prenatal and Postnatal Depression Scales, both of which have been used extensively with the target population.

Anxiety will be assessed with the Generalized Anxiety Disorder Scale (GAD-7)², a psychometrically sound instrument routinely used in general health care settings.

Stress will be assessed with the Perceived Stress Scale,³ a psychometrically sound instrument that has been used in other studies of contemplative interventions with pregnant women⁴⁻⁷.

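### The chart retention score accepts either agonist in urine whatever was prescribed, and counts counselling weeks with no per-woman denominator, so non-prescribed use can be scored as adherence

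*Combined protocol and SAP*

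**What the plan says.** Section 6.2 (clinical record indicators) defines MOUD treatment retention, a primary endpoint, as a composite of two counts taken over a window described as "throughout the prenatal period to 3 months postpartum". The medication count is the "number of weeks buprenorphine or methadone present in the urine toxicology report". The counselling count is the "number of weeks attended required counseling as part of comprehensive treatment as usual, as indicated in clinical notes". No rule for combining the two is given.

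Opioid abstinence, the other primary endpoint, comes from the same weekly urine screen, which is run "to assess for THC, cocaine, benzodiazepines, methamphetamine, opioids, methadone and buprenorphine". Methadone and buprenorphine are thus separate lines from opioids. Section 2.1 describes standard care as "medication for opioid use disorder (MOUD) with methadone or buprenorphine", so either drug may be the one a given woman is prescribed.

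Section 5.1 describes usual care thus: "Such treatment includes medication for opioid use disorder, individual and/or group counseling, and case management". It states no counselling frequency. The survey in section 6.2 offers the options "every week, every other week, once a month, less than once a month", which record attendance and not requirement.

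Nothing later ties the counts to prescription or requirement. Section 5.4 tracks adherence to usual care without a denominator. Section 9.5.1 gives no scoring rule. Section 9.6 takes the number of weeks retained into a t-test or Wilcoxon test, and a binary retention outcome into a logistic GEE model.

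**The concern.** Adherence means taking what was prescribed and attending what was required. The medication count does not look at the prescription. For a woman prescribed buprenorphine, urine positive for methadone alone shows that her own medication was not detected and another opioid agonist was, yet the week scores as fully adherent. If abstinence is read from the opioid line of the panel only, that week also counts as abstinent.

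The counselling count restricts which sessions are counted but does not divide by how many were due. It therefore mixes how well a woman complied with how much was asked of her.

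Both features blur the contrast in a primary endpoint, in a trial planned at 80% power with little to spare.

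**Working it through.** **1. The plan's own figures.** Inputs from sections 4.3 and 9.2: 150 recruited, 20% attrition, equal allocation, 3 timepoints, within-person correlation 0.5, two-sided 0.05 (stated there for the weeks-abstinent comparison).

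- Analysed: 150 × 0.80 = 120, or 60 per arm.
- Repeated-measures factor: (1 + (3 − 1) × 0.5)/3 = 0.667, so effective n = 60/0.667 = 90 per arm.
- Normal-approximation power for two proportions: 60% vs 79.2% gives 80.5%; 70% vs 87% gives 79.8%; 80% vs 94% gives 80.3%.

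The stated 80% reproduces, so there is no arithmetic error. These figures rest on a percentage of women retained or abstinent, not on the week counts of section 6.2.

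**2. The medication and abstinence rules applied to one week.** Take a woman prescribed buprenorphine whose panel is otherwise negative.

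| Urine shows | Medication week as written | Abstinent week |
|---|---|---|
| Buprenorphine | counts | must be abstinent, or no adherent woman could ever be |
| Methadone only | counts | not stated; abstinent if only the opioid line decides |
| Neither | does not count | abstinent |

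The first and second rows score the same on medication. The first row also shows that prescribed agonists must be kept out of the opioid-positive definition. The plan therefore needs a rule separating prescribed from non-prescribed agonists, and it has none.

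**3. The counselling count.** Over a window of W weeks, a woman required weekly outscores a fully compliant woman required every f weeks once she attends floor(W/f) + 1 weeks. Both W and f are assumptions. For example, enrolment at 28 weeks, delivery at 39 and 13 weeks postpartum give W = 39 − 28 + 13 = 24.

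- W = 24, f = 2: 13 of 24 (54%) outscores 12 of 12 (100%).
- W = 24, f = 4: 7 of 24 (29%) outscores 6 of 6.
- W = 39: the thresholds are 20/39 = 51% and 10/39 = 26%.

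These reversals concern the counselling component alone.

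**4. Illustrative sizes on assumptions the documents do not supply.**

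*Medication.* Suppose a share m of truly non-retained women is scored as retained in both arms. Observed retention is p + (1 − p)m, and the arm difference shrinks by the factor (1 − m).

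| m | TAU | MMORE | Power (effective n = 90 per arm) |
|---|---|---|---|
| 0 | 60.0% | 79.2% | 80.5% |
| 5% | 62.0% | 80.2% | 77.5% |
| 10% | 64.0% | 81.3% | 74.3% |
| 20% | 68.0% | 83.4% | 67.3% |

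*Counselling.* A simulation used 60 per arm, attendance probabilities drawn from beta distributions with means 0.60 and 0.7281 (parameters summing to 3), and windows of either 27 weeks or 22 to 38 weeks. If every woman is required weekly in equal windows, raw weeks and attended share both have 81% power. If 20% of women have a less-than-weekly requirement (half every 2 weeks, half every 4), raw weeks fall to 52–58% while attended share keeps 79–80%. With weekly requirements for all but windows of 22 to 38 weeks, raw weeks have 74%. That last case matters if counting starts at enrolment, since section 3 says "We will aim to recruit women in their 2nd/early 3rd trimester of pregnancy".

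**The case against.** The strongest reply is that much of this depends on facts the documents do not contain. No section says that required counselling frequency differs between women or practices; section 5.1 describes format, and the survey categories describe attendance. The counselling reversal is therefore conditional. It is also shown for one component only: without a combining rule, nobody can say whether the composite reverses. The urine panel is a list of analytes, not a scoring rule. The chart template named in section 10.1 is not reproduced, so the prescribed agent may already be abstracted. Retention and abstinence also have self-report measures. All of this stands. It does not reach the either-drug rule, which is explicit: even if the template records the prescription, the stated score does not use it, and the self-report item on skipped doses is not part of the chart score.

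Three stronger readings are tempting and not supported.

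- A reader might infer that the measure moves against MMORE, because more stable women would be asked to attend less. No section says practices reduce the requirement for stable women. Under equal randomisation the expected effect is mainly noise and attenuation.
- A reader might infer that both primary endpoints are definitely wrong for such a week. For abstinence the documents support only that it may be misclassified, because the rule is unstated.
- A reader might apply a share of misclassified weeks to the planned 80% vs 94% abstinent. Those are percentages of women, so the units do not match without a rule from weeks to the binary outcome.

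A further fair objection concerns the obvious repair. Attended over required, computed only while a woman is in treatment, gives 100% to one who leaves after 2 of 2 sessions. That would defeat a retention endpoint, so the denominator has to run on.

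**Conclusion.** The concern holds for the medication component as written: a week showing only a non-prescribed agonist scores as adherence, and no other section corrects this. It may hold for abstinence, where the plan does not say how such a week is classified. For counselling it holds conditionally: if required frequency differs between women, that component can rank a partly compliant woman above a fully compliant one.

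The likely consequence is misclassification and a diluted arm difference. Its size is unknown, because the documents give no rate of non-prescribed agonist use, no required counselling frequency and no rule turning weeks into the binary GEE outcome. The power figures under point 4 of the check show sensitivity and are not estimates. The medication illustration also assumes the same misclassification share in both arms.

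**What to change.** Change the scoring only; care is unaffected. In section 6.2, section 9.5.1 and the clinical record template:

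1. Abstract the agent prescribed in each week, allowing for documented switches, and count a medication week only when that agent is present in the urine.
2. For abstinence, count methadone or buprenorphine that is not prescribed as an opioid-positive week.
3. As a supporting analysis, where the notes give the required frequency, score counselling as weeks attended over weeks required across the whole window to 3 months postpartum. Keep weeks after leaving treatment in the denominator as not attended. With a weekly requirement over 24 weeks, leaving after 2 of 2 then scores 2/24 = 8%, not 100%. State in advance which required frequency applies to those later weeks. Supporting status is appropriate because the requirement may itself change after randomisation.

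The cost is slightly longer chart abstraction and a written scoring rule, fixed before unblinded analysis. Required frequency may be missing from some notes; report how often.

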4. SELECTION AND ENROLLMENT OF PARTICIPANTS

4.1 Inclusion Criteria

Eligible participants will be women, 18 years of age or older, English-speaking, carrying a singleton pregnancy, and receiving medication for OUD treatment as part of prenatal care at a partner maternity care practice.

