6.2.2 Enrollment, Baseline, and/or Randomization

Enrollment

In this study, the enrollment date will be the date that all of the screening criteria were met, and the individual consents to participate.

Baseline Assessments

Participants will complete the baseline assessment upon consenting to participate in the study. The project coordinators will administer the baseline assessment to the participant through a secure online survey. For participants who do not wish to complete the survey online, the project coordinator will arrange for either a phone interview with the participant to complete the survey or will mail the participant the survey along with a self-addressed and stamped envelope for the participant to return the survey. Both forms of the assessment will be coded with a unique study ID.

Randomization

Following baseline completion, participants will be randomized to condition by the lead project coordinator. The lead project coordinator will meet via phone with participants assigned to the MMORE condition to explain the condition. Participants in the MMORE condition will receive a secure password-protected access to the digital companion features.

Randomization will be conducted via permuted blocks. Once 8-10 participants have enrolled, an intervention will commence for that cohort. The randomization block size would be random, with blocks of size 4, 6, and 8. In thinking about how best to implement our group randomization plan in the context of the reality of recruitment of this high-risk target population, we have developed a plan of ongoing recruitment and starting a new group at least every 8 weeks. With a conservative recruitment

rate of 12 participants per month, we do not anticipate a good deal of differential lag-time between recruitment into the study, completion of baseline, randomization, and start of a new group.

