9.2 Sample Size and Randomization

Sample Size.

Aim 1: For the longitudinal models of binary outcomes (abstinence, retention), assuming a within-person correlation of 0.5, there will be 80% power to detect difference between arms in the proportion retained at the 3 timepoints if the average percentage retained in the TAU arm is 60%, and the average percentage retained in the MMORE arm is 79.2%. Similar power is obtained if the TAU arm has a retention percentage of 70% while the MMORE arm has a percentage of 87% across the three timepoints. In terms of comparing abstinence longitudinally, there will be 80% power to detect a difference between arms in the percentage abstinent at the 3 timepoints if the average percentage abstinent in the TAU arm is 80% while in the MMORE arm is 94%. Power for the comparison of number of weeks abstinent during the 8-week intervention period will be 80% (at the two-sided 0.05 significance level) for differences between arms that are 0.52 times a standard deviation or more. Analyses testing for differences between arms in changes between baseline and 8-weeks, will have 80% power to detect differences that are 0.40, 0.52, and 0.61 times a standard deviation, assuming within-person correlations of 0.7, 0.5, and 0.3, respectively. We will aim to recruit 150 participants to allow for attrition (20%).

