9.5 Outcomes

9.5.1 Primary Outcome

Treatment Retention. Operationalized as adherence to medication for opioid use disorder and retention in treatment over time.

Opioid use abstinence. Operationalized as number of weeks of consistent abstinence from opioids over the study period and continuity of abstinence from one assessment time point to the next.

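### The chart retention count, read literally, includes weeks before randomisation, and the abstinence count has no consistent window; the cost is power in the weeks-retained test, not bias in raw weeks

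*Combined protocol and SAP*

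**What the plan says.** Section 6.2 defines both primary endpoints from the clinical record as numbers of weeks. Retention combines weeks with buprenorphine or methadone in urine and weeks of counselling attended, "throughout the prenatal period to 3 months postpartum". Abstinence is the "number of weeks consistently abstinent from opioids over the perinatal period to 3 months postpartum". Perinatal is not defined.

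Other sections give other windows. Section 9.5.1 counts abstinence as "number of weeks of consistent abstinence from opioids over the study period" and describes retention with no start or end: "Operationalized as adherence to medication for opioid use disorder and retention in treatment over time". Section 9.2 says "Power for the comparison of number of weeks abstinent during the 8-week intervention period will be 80" per cent for a difference of 0.52 SD.

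On timing, section 3 says "We will aim to recruit women in their 2nd/early 3rd trimester of pregnancy". Section 4.1 requires that women be "receiving medication for OUD treatment as part of prenatal care at a partner maternity care practice". Section 6.2.2 says "Following baseline completion, participants will be randomized to condition by the lead project coordinator".

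Section 9.6 analyses binary abstinence and retention at 8 weeks and at 3 months postpartum by logistic GEE with baseline covariates. Separately, it compares number of weeks retained between arms by an unadjusted t-test or Wilcoxon test. It lists no test of weeks abstinent.

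**The concern.** A woman who enters in mid-pregnancy already on MOUD has chart weeks that precede her allocation. Counting the whole prenatal period scores those weeks as outcome, although MMORE cannot have changed them. They add between-woman variation to the weeks-retained comparison without adding any expected difference between arms.

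For abstinence the problem is that the window is not fixed. Three sections give three descriptions, and they would produce different numbers from the same chart.

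The start date also should not be left to the extraction stage. Section 6.2 assigns chart review to the lead project coordinator, whom section 6.2.3 lists as un-blinded.

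**Working it through.** **1. The plan's own figure.** Section 9.2 gives 150 recruited, 20% attrition, two-sided 0.05 and a 0.52 SD difference. Evaluable: 150 × 0.80 = 120, or 60 per arm. Power = Φ(d × √(n/2) − 1.96) = Φ(0.52 × √30 − 1.96) = Φ(0.888) = 81% (80.6% by the t distribution). The stated 80% reproduces. It applies to an 8-week count after randomisation, not to the window in 6.2.

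**2. What weeks before randomisation do to a raw count.** Let the total be post-randomisation weeks plus pre-randomisation weeks.
- Expected difference between arms: unchanged, because randomisation balances the pre-randomisation part in expectation.
- Spread: with k = pre/post and pre–post correlation r, SD(total)/SD(post) = √(1 + k² + 2rk).
- Standardised effect: 0.52 / √(1 + k² + 2rk).

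**3. Assumptions not in the documents.** Chart counting starts at week 8 or 12; delivery is at week 40; the postpartum part is 13 weeks; SD is proportional to window length; all women enter at the same week; r is 0.3 to 0.7; and the 0.52 SD of section 9.2 applies to the count from randomisation to 3 months postpartum.

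**4. Worked case.** Chart start week 12, entry week 28: pre = 28 − 12 = 16, post = (40 − 28) + 13 = 25, k = 0.64. At r = 0.5 the SD factor is √(1 + 0.41 + 0.64) = 1.43, the effect is 0.52/1.43 = 0.363 SD, and power is 51%.

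**5. Range.**

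| Chart start | Entry week | Pre / post weeks | Pre share | Effect (SD), r = 0.3 / 0.5 / 0.7 | Power, r = 0.3 / 0.5 / 0.7 |
|---|---|---|---|---|---|
| 12 | 14 | 2 / 39 | 5% | 0.512 / 0.507 / 0.502 | 80.0% / 79.2% / 78.5% |
| 12 | 20 | 8 / 33 | 20% | 0.474 / 0.456 / 0.440 | 73.7% / 70.4% / 67.3% |
| 12 | 28 | 16 / 25 | 39% | 0.388 / 0.363 / 0.342 | 56.6% / 51.2% / 46.6% |
| 8 | 14 | 6 / 39 | 13% | 0.492 / 0.479 / 0.467 | 76.9% / 74.7% / 72.5% |
| 8 | 20 | 12 / 33 | 27% | 0.447 / 0.425 / 0.406 | 68.8% / 64.4% / 60.4% |
| 8 | 28 | 20 / 25 | 44% | 0.357 / 0.333 / 0.313 | 49.8% / 44.6% / 40.3% |

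**6. Mixed entry weeks.** With entry spread evenly over weeks 14 to 30, and weekly retention propensity with mean 0.75 and SD 0.25 (before truncation to 0–1), the effect is 0.43 to 0.51 SD and power 66% to 80%. The top of the loss in step 5 is therefore a late-entry case, not a typical one. Part of the reason is that a raw count from randomisation already varies with each woman's length of follow-up.

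**7. If a share of weeks were used.** The difference would be multiplied by post/(pre + post). With chart start at week 12 that is 39/41 = 0.95 for entry at week 14, 33/41 = 0.80 at week 20 and 25/41 = 0.61 at week 28.

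**The case against.** A reader might infer that both primary endpoints are counted from the start of prenatal care, that the effect is therefore biased towards zero, and that the main analysis is diluted. The documents do not support this stronger reading, for four reasons.

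- **Both endpoints.** The phrase about the prenatal period belongs to retention. Abstinence uses an undefined term, and the windows in 9.2 and 9.5.1 would on an ordinary reading exclude weeks before enrolment. For abstinence the fault is inconsistency, not a demonstrated early start.
- **Bias.** Section 6.2 defines numbers of weeks. The expected difference in weeks is the same with or without the earlier weeks. Shrinkage applies only to a share of weeks, which no section defines.
- **Main analysis.** The GEE uses binary status at two time points after randomisation, and nothing derives that status from the counts. Equally, no other rule for the binary status is given, so the link cannot be ruled out.
- **Intent.** The retention wording could loosely mean prenatal follow-up after entry. The schedule in 6.1 lists both outcomes at baseline as well as later, which gives status at entry its own place.

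These points stand and limit the concern. They do not remove it. No section starts either count at randomisation, and a primary endpoint should not depend on a charitable reading. It is also fair that the size of the loss rests on assumed values and is negligible for early entry.

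**Conclusion.** The concern holds in a limited form. As written, the retention count takes in weeks before randomisation, and the abstinence window is undefined and inconsistent across three sections. The consequence is lost precision in the weeks-retained test: about 40% to 80% power against 81% for a 0.52 SD effect with 60 per arm, over entry weeks 14 to 28, chart starts at week 8 or 12 and correlations of 0.3 to 0.7. The direction is the same throughout; the size cannot be fixed, because the documents give no SD for the count, no distribution of entry week and no chart start. The figures are for the t-test; the Wilcoxon test was not calculated separately. The raw difference in weeks is not biased, and the GEE is untouched unless its binary status comes from these counts. The windows should be settled before any chart is extracted.

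**What to change.** In 6.2, start both chart counts at the date of randomisation and end them at 3 months postpartum. Make 9.2, 9.5.1 and 9.6 use the same window; in 9.2 this means restating power for that window in place of the 8-week count. In 9.6, state whether the binary GEE status is derived from the counts and, if so, how.

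Use the chart record before randomisation (share of weeks with MOUD in urine, share abstinent) only as a baseline covariate, and replace the unadjusted weeks-retained comparison with a model adjusted for it. Used this way the earlier weeks help: at a pre–post correlation of 0.5 the residual SD factor is √(1 − 0.25) = 0.866, the effect becomes 0.52/0.866 = 0.60 SD, and power is Φ(0.60 × √30 − 1.96), about 91%, under the common-entry-week assumption.

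Starting at randomisation leaves women with different lengths of follow-up: under the assumptions above, 39 weeks for entry at week 14 and 25 weeks for entry at week 28. The count therefore also needs either a common window or a denominator equal to each woman's weeks from randomisation to 3 months postpartum.

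The cost is a wording change in four sections, one date filter in the chart extract and one adjusted model. No new data source is needed.
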